The Durata® family of ICD leads utilizes a silicone polyurethane co-polymer insulation known as Optim which has been associated with a significant reduction in abrasion when compared to Riata and Riata ST silicone insulated leads. Although the incidence of these insulation abrasion issues is extremely low in Durata leads, the Durata leads are being included in this study for comprehensive

analysis across all St. Jude Medical ICD lead types. This study aims to prospectively determine the prevalence and incidence of lead compromise evidenced by imaging (includes externalized conductors and other visual lead anomalies, by each subcategory, as listed in Appendix A) and electrical dysfunction in patients with Riata, Riata ST silicone ICD, QuickSite/QuickFlex CRT and Durata ICD leads. Prevalence as well as incidence of externalized conductors and other visual lead anomalies will be separately analyzed and reported. In addition, this study will provide information to the physicians regarding the possibility that an observation of externalized conductors with normal electrical function may progress to an electrical malfunction. The SJM Cardiac Lead Assessment Study is sponsored by St. Jude Medical (SJM) and constitutes the modification of the “Riata Lead Evaluation Study”.

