*Expected attrition in each of the lead groups is based on the rationale provided above the table as well as larger attrition expected in older leads.

[figure not shown]
At enrollment, medical history, demographic data and lead measurement data will be collected. Additionally, cinefluoroscopy (AP, LAO 45° or the best possible LAO view, RAO 45° or the best possible RAO view) will be performed to determine the prevalence of lead compromise. A copy of

cinefluoroscopy performed as part of separate screening can be used to determine the prevalence of lead compromise as long as all three views (AP, LAO 45° or the best possible LAO view, RAO 45° or the best possible RAO view) are available. In patients with evidence of externalized conductors or other visual lead anomalies (fracture, subclavian crush, kink, broken filars on a shocking coil and other irregularities) the following chest x-rays or other available imaging studies will be collected (if available): a) earliest imaging study showing evidence of externalized conductors or other visual lead anomaly and b) latest imaging study that does not show any evidence of externalized conductors or other visual lead anomaly

Data will be collected at 6, 12, 18, 24, 30, and 36 months post enrollment and during any unscheduled follow-up visits due to patient symptoms suggestive of or with evidence of lead electrical problems. Additionally, cinefluoroscopy (AP, LAO 45° or the best possible LAO view, RAO 45° or the best possible RAO view) will be performed in all patients to determine the incidence and mechanical progression of externalized conductors at the 12, 24, and 36 month visits.

During any follow-up visits, device data and stored electrograms will be collected. All clinical events such as hospitalizations, emergency room visits, and adverse events will also be collected. All study data, including device data and stored electrograms will be sent to SJM electronically. If any lead being followed in this study develops a significant electrical abnormality suggestive of lead malfunction and x-ray or cinefluoroscopy would be performed as per the site standard of care then copies of x-ray or cinefluoroscopy should be submitted to SJM.

During the course of the study, any explanted leads should be returned to Returned Goods, St Jude Medical, Sylmar, CA, for analysis.

Study Flow Diagram

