3.2.2.8 Time from other visual lead anomalies by each subcategory to clinical intervention

Lead Population

All the leads with other visual lead anomalies (by each sub category) within the Riata, Riata ST silicone, QuickSite/QuickFlex (1056T, 1058T, 1156T, 1158), and Durata lead groups

Analysis:

Time to clinical intervention will be analyzed using the Kaplan-Meier method. The zero time will be the date at

which other visual lead anomaly (by each subcategory) was detected. Those patients who experience other visual lead anomaly (by each subcategory) after enrollment but do not experience clinical intervention will be censored 3 years after enrollment in this trial. A separate Kaplan-Meier curve will be calculated for each of the lead subgroups outlined in Table 2.

For QuickSite/QuickFlex leads only, data from patients with an additional 1 year of follow-up will contribute to 2 separate lead subgroups (See Section 3.4.5).

3.2.2.9 Comparison of patients with lead compromise as evidenced by imaging (includes externalized conductors and other visual lead anomalies by each subcategory) to those without lead compromise

Patient Population

All the patients within the Riata, Riata ST silicone, QuickSite/QuickFlex (1056T, 1058T, 1156T, 1158) and Durata lead subgroups.

Analysis

Demographic and clinical parameters will be compared between patients who experience a lead compromise as evidenced by imaging and those who do not experience a lead compromise. Specifically, the variables age, gender, body mass index, lead size, lead model, and implant factors such as venous access site, number of other leads in the vasculature, fixation location in the right ventricle, level of activity (based on functional NYHA class scale I, II, III, IV), level of therapy that patient received (no ATP/shock, ATP or shock) and slack (grades 0, 1, 2, 3, 4 based on the scale described by Ha et al., 2010¹²) in the lead will be used for the comparison. Continuous variables such as age or body mass index will be compared using Student's T-tests while categorical variables such as gender or lead models will be compared using Pearson's Chi-square statistic. Point estimates and p-values will be provided from these analyses.

3.2.2.10 Comparison of patients with electrical dysfunction to those without electrical dysfunction.

Patient Population

All the patients within the Riata, Riata ST silicone, QuickSite/QuickFlex (1056T, 1058T, 1156T, 1158) and Durata lead subgroups.

Analysis

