Demographic and clinical parameters will be compared between patients who experience electrical dysfunction and those who do not experience electrical dysfunction. Specifically, the variables age, gender body mass index, lead size, lead model, and implant factors such as venous access site, number of other leads in the vasculature, fixation location in the right ventricle, level of activity (based on functional NYHA class scale I, II, III, IV), level of therapy that patient received (no ATP/shock, ATP or shock) and slack in the lead (grades 0, 1, 2, 3, 4 based on the scale described by Ha et al, 2010¹²) will be used for the comparison. Continuous variables such as age or body mass index will be compared using Student's T-tests while categorical variables such as gender or lead models will be compared using Pearson's Chi-square statistic. Point estimates and p-values will be provided from these analyses.

In addition, the two patient groups will be compared for the following endpoints:

1. Frequency of externalized conductors. This will be done using a Pearson's Chi-square analysis.
2. Frequency of other visual lead anomalies. This will be done using a Pearson's Chi-square analysis.
3. Time to detection of externalized conductors. A Kaplan-Meier analysis will be used for this comparison.
4. Time to detection of other visual lead anomalies. A Kaplan-Meier analysis will be used for this comparison.
5. The extent of externalization will be compared using Pearson's Chi-square analysis.
6. Number of zones with externalization within one lead will be compared using a Student's T-test.
7. Location of externalization will be compared using Pearson's Chi-square analysis.
8. Amount of slack in the lead (based on the scale described by Ha et al, 2010)¹² will be compared using Pearson's Chi-square analysis.

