11.2 Cinefluoroscopy Adjudication Committee

Cinefluoroscopy Adjudication Committee (CAC) will be comprised of at least three Electrophysiologists or Cardiologists specially trained in using Cinefluoroscopy in this patient population. The role of the CAC is to adjudicate the cinefluoroscopy videos/images to determine the presence of lead compromise in the SJM Cardiac Lead Assessment study patient population. Committee members will be reviewing the cinefluoroscopy videos/images for the enrollment, 12, 24, and 36 month follow-up visits and any additional cinefluoroscopy videos/images received during the course of the study. Data will be sent either electronically or on a disk to the committee members. Once the adjudication is complete, a cinefluoroscopy adjudication form will be collected per patient per study visit. If the presence of externalized conductors is deemed to be ‘indeterminate’ then the cinefluoroscopy will be further reviewed by two other CAC members. Sample pictures/fluoros/x-rays and other examples of “other visual lead anomalies” will be provided to the adjudication committee to aid the committee members in identifying these “other visual lead anomalies” on the cinefluoroscopy videos/images received from the site.

Only the adjudicated imaging data will be included in the post market surveillance reports. Percentage of leads with compromise, evidenced by imaging, will be presented in the report. The type, extent and location of

lead compromise, as described in Appendix A, will also be included. As detailed in Appendix A, each region of the HV as well as CRT leads is divided into different regions. Both the proximal as well as distal ends of externalization will be recorded by the cinefluoroscopy adjudication committee. The distribution of externalization (both absolute number and percentage) by each region of the lead will be presented for both proximal and distal ends of externalization. The distribution of “other visual lead anomalies” (both absolute number and percentage) by each region of the lead and each individual subcategory of “other visual lead anomalies” will be presented. The frequency (both absolute number as well as percentage) of individual subcategories will be reported for “other visual lead anomalies”.

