Appendix A: Details About Lead Compromise

[figure not shown]
Lead Compromise as evidenced by imaging includes externalized conductors or other visual lead anomalies. The types, extent and location of these anomalies in high voltage (HV) leads are listed below:

Type	Extent	Location on the lead (see figure below)
Externalized Conductors	- Apparent width and length of externalized conductors on fluoroscopy	- Region 1 - Region 2 - Region 3 - Region 4
Other Visual Lead Anomalies	- Fracture - Subclavian crush - Kink - Broken filars on a shocking coil - Other irregularities	- Region 1 - Region 2 - Region 3 - Region 4 - RV coil - SVC coil - Distal to RV coil - Proximal to region 1

Similarly, the type, extent and location of these anomalies in CRT leads are listed below:

Type	Extent	Location on the lead (see figure below)
Externalized Conductors	- Apparent width and length of externalized conductors on fluoroscopy	- Region a - Region b - Region c - Region d
Other Visual Lead Anomalies	- Fracture - Kink - Subclavian crush - Other irregularities	- Region a - Region b - Region c - Region d

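### Section 3.2.2.9: the heading points to anomaly subcategories, but the analysis paragraph sets one pooled lead-compromise split, so factors specific to externalized conductors can be diluted

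*Combined protocol and SAP*

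**What the plan says.** The analysis paragraph of section 3.2.2.9 sets a two-group comparison at patient level: "Demographic and clinical parameters will be compared between patients who experience a lead compromise as evidenced by imaging" and those who do not. It lists age, sex, body mass index, lead size and model, venous access site, number of other leads, fixation location, activity level, therapy received and slack. It plans t-tests or chi-square tests with point estimates and p-values. No alpha, power or effect size is given.

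The heading of the same section describes the event differently: "includes externalized conductors and other visual lead anomalies by each subcategory) to those without lead compromise".

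Appendix A gives the definition: "Lead Compromise as evidenced by imaging includes externalized conductors or other visual lead anomalies". For high-voltage leads the other anomalies are fracture, subclavian crush, kink, broken filars on a shocking coil and other irregularities. The list for CRT leads is the same without broken filars.

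On prevalence and incidence, the Introduction commits to separation: "Prevalence as well as incidence of externalized conductors and other visual lead anomalies will be separately analyzed and reported".

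**The concern.** Following the analysis paragraph literally, a patient with a kinked lead and a patient with externalized cables are the same case. The Introduction attributes externalization to abrasion from inside the lead and names subclavian crush separately as a cause of insulation defects. The listed factors therefore need not act alike on both.

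Two things are at stake. A factor that raises only the risk of externalization would be pulled toward no effect in the pooled table. A factor that acts only on another anomaly could be reported as a factor for lead compromise in general. Also, because heading and paragraph can be read differently, the choice between a pooled and a split comparison could be made after the data are seen.

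**Working it through.** **Text check.** The numbered imaging outcomes come in pairs, one for externalized conductors and one for other visual anomalies by subcategory: 3.2.1.2 and 3.2.1.3 (prevalence), 3.2.1.5 and 3.2.1.6 (hazard rates), 3.2.2.1 and 3.2.2.2 (time from enrollment), 3.2.2.4 and 3.2.2.5 (time to electrical dysfunction), 3.2.2.7 and 3.2.2.8 (time to intervention). Section 3.2.2.10 also separates them, with an item headed "Frequency of externalized conductors" and another for other anomalies. Its groups, however, are defined by electrical dysfunction, so it does not ask which patients develop externalization. Only 3.2.2.9 compares the listed factors by imaging finding, and its paragraph uses the union.

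**Size.** The plan states no figure for 3.2.2.9, so there is none to reproduce. The following is an illustration.

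Inputs:
- n = 560, the sum of the Riata target enrollments in Table 2 (195 + 185 + 180), taking one such lead per patient.
- Assumed: factor present in 40% (224 with, 336 without), and true odds ratio 2.0 for externalization.
- Assumed: other anomalies occur at rate k, unrelated to the factor and independent of externalization.
- Assumed externalization rate without the factor, e0: 10%, 20% and 33.3%. The Introduction reports 0.5% to 33.3% for Riata/Riata ST.
- k is not in the documents, so a range of 1% to 20% is shown.

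Formulas: odds of e1 = 2.0 × e0/(1 − e0). Merged risk c = 1 − (1 − e)(1 − k) at each factor level. Merged odds ratio = [c1/(1 − c1)] / [c0/(1 − c0)]. Power is the two-sided 5% normal approximation for two proportions, with pooled variance under the null.

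Worked case, e0 = 10%, k = 5%:
- e1 = 0.2222/1.2222 = 0.1818.
- c0 = 1 − 0.90 × 0.95 = 0.1450 and c1 = 1 − 0.8182 × 0.95 = 0.2227.
- Merged odds ratio = 0.2866/0.1696 = 1.69.
- Power: difference 0.0777, null standard error 0.0329, alternative standard error 0.0338, so Φ[(0.0777 − 1.96 × 0.0329)/0.0338] = 65%.

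| e0 | k | Merged odds ratio | Power, externalization alone | Power, merged |
|---|---|---|---|---|
| 10% | 1% | 1.92 | 79% | 76% |
| 10% | 5% | 1.69 | 79% | 65% |
| 10% | 10% | 1.53 | 79% | 54% |
| 10% | 20% | 1.36 | 79% | 38% |
| 20% | 5% | 1.83 | 94% | 90% |
| 33.3% | 5% | 1.91 | 98% | 96% |

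**Shared factor.** If the factor also doubles the odds of other anomalies (e0 = 10%, k = 5% without the factor), then k with the factor is 0.1053/1.1053 = 0.0952. This gives c0 = 0.1450, c1 = 1 − 0.8182 × 0.9048 = 0.2597 and a merged odds ratio of 2.07. There is no dilution.

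**Larger sample.** Dilution does not shrink with n. With 1,500 leads, a 50:50 factor and average externalization of 5%, the odds ratio of 2.0 becomes 1.41 at k = 5% and 1.26 at k = 10%, and power falls from 81% to 51% and 35%. At 0.5% externalization, power is only 15% even when externalization is analysed alone, so splitting cannot rescue that case.

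**Proposed reference group.** Against patients free of any compromise, the odds of externalization are e/[(1 − e)(1 − k)]. The (1 − k) term cancels between factor levels and the odds ratio stays at 2.0. Power falls somewhat below the alone column, because patients with only other anomalies leave the comparison.

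**The case against.** The strongest reply is that the heading already promises subcategories. Wherever else the numbered outcomes use that phrase they mean separate analyses, and in a simple any-versus-none comparison it would do no work. This stands in part. It makes the problem a conflict between heading and analysis text. A reader might infer a deliberate decision to pool, and the documents do not support that. The conflict still needs resolving, because the paragraph is the operative text and names no reference group for split comparisons.

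A reader might also infer that the two kinds of finding are kept apart throughout the rest of the plan. They are not. Section 3.1 says enrollment imaging "will be performed to determine the prevalence of lead compromise", and section 11.2 says "Percentage of leads with compromise, evidenced by imaging, will be presented in the report", alongside a breakdown by type. The contrast holds among the numbered outcome measures only. The Introduction's commitment to separate analysis covers prevalence and incidence, so it bears on this comparison only by analogy.

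Nor is 3.2.2.9 the sole description of where externalization occurs. Sections 3.2.1.2, 3.2.1.5 and 3.2.2.1 report externalization alone by lead group or lead-age subgroup. What is missing is narrower: a comparison on the patient and implant factors.

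Finally, the Introduction never mentions kinks and does not discuss risk factors by mechanism, so type-specific effects are an assumption. The consequence is also limited: this is a secondary, univariate comparison on which no primary outcome depends.

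**Conclusion.** The point holds as a drafting conflict with an analytic consequence. As the paragraph stands, the event is mixed, and no other section compares the listed factors for externalization alone.

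The size is conditional. Under the stated assumptions the loss is small when externalization is common or other anomalies are rare (odds ratio 1.91 at 33.3% with 5%; 1.92 at 10% with 1%). It is material when other anomalies are about as common as externalization or more so (1.53 and 1.36 at 10% with 10% and 20%). The documents give no rate for other anomalies, so they do not show which case applies.

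One further inference should not be drawn: that the Durata comparison would be almost entirely about other anomalies. The protocol expects very little insulation abrasion in Durata, but it gives no rate of other anomalies in that lead.

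**What to change.** Rewrite the analysis paragraph of 3.2.2.9 so that the patient-level comparison is run separately for (a) externalized conductors and (b) each subcategory of other visual anomaly. Run it within each lead group, with patients free of any imaging compromise as the reference. Where a subcategory is too sparse to test, show counts only, and fix the minimum number of cases before the data are examined. Keep the pooled comparison as a descriptive supplement.

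No new data are needed, since the cinefluoroscopy committee already records type, extent and location. The cost is revised wording, more tables, more descriptive p-values and some small cells.

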2.0 Purpose

The objectives of the study are:

1. To determine the prevalence of externalized conductors at enrollment in Riata®, Riata® ST Silicone, QuickSite®/QuickFlex® and Durata® leads
2. To determine the prevalence of other visual lead anomalies by each subcategory per Appendix A at enrollment in Riata®, Riata® ST Silicone, QuickSite®/QuickFlex® and Durata® leads
3. To determine the prevalence of electrical dysfunction[§] at enrollment in Riata®, Riata® ST Silicone, QuickSite®/QuickFlex® and Durata® leads
4. To determine the incidence of externalized conductors after enrollment in Riata®, Riata® ST Silicone, QuickSite®/QuickFlex® and Durata® leads
5. To determine the incidence of other visual lead anomalies by each subcategory per Appendix A after enrollment in Riata®, Riata® ST Silicone, QuickSite®/QuickFlex® and Durata® leads
6. To determine the incidence of electrical dysfunction[§] after enrollment in Riata®, Riata® ST Silicone, QuickSite®/QuickFlex® and Durata® leads.
7. To evaluate the 30-day adverse event rate associated with lead revision procedures (include lead extractions or abandonments with or without lead replacement) in Riata®, Riata® ST Silicone, QuickSite®/QuickFlex®, and Durata® families of leads
8. To determine the prevalence of “other insulation anomalies” in “returned leads” for Riata®, Riata® ST Silicone, QuickSite®/QuickFlex®, and Durata® families of leads. “Other insulation anomalies” include any of the following:
 - Internal abrasion short under RV shock coil
 - Internal abrasion short under SVC shock coil
 - Exposed conductors defined as a breach of the outer insulation
 - Breach of the internal silicone lumen tubing, but the conductor cable is contained within the lead body diameter.

[§]”Electrical dysfunction” is determined to be present after adjudication of the following cases of potential electrical failures that led to the lead being either

surgically capped/extracted or electrically abandoned. Potential electrical failures include the following:

- Presence of non-physiologic noise not due to external interference
- Rise in pace/sense (p/s) conductor impedance to $> 2000 \Omega$ or increase of more than 200Ω over previous 6 months or increase of 400Ω over any period of time
- Decrease of more than 200Ω over previous 6 months or to impedance $< 200 \Omega$ from baseline impedance $> 300 \Omega$ or decrease of 400Ω over any period of time

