Assuming an annual mortality of 7% in the ICD patient population, the mortality at 3 years is 20% $[1 - (1-0.07)^3]$ In the recent RHYTHM ICD/QuickSite 1056K left heart lead study, the annual mortality was 12.8%, which would result in a mortality of 33.7% $[1 - (1-0.128)^3]$ at 3 years. If the ICD:CRT-D device mix is 60%:40% then the expected overall mortality in this study at 3 years is 25.5% ($=0.6 \times 0.20 + 0.4 \times 0.337$).

Withdrawals due to reasons other than death

In an ongoing St. Jude Medical post-approval study (SJ4 PAS), the attrition rate due to reasons other than death at 22 months of follow-up is 9%. Thus, it is anticipated that the attrition rate at 3 years for reasons other than death will be 15%.

Assuming that deaths and withdrawals are independent events, the total attrition is expected to be approximately 37% ($= 1 - (1-0.255) \times (1-0.15)$) over 3 years.

Since the Riata/Riata ST leads are recalled, it is more likely that some physicians will explant them, even when electrical function is normal. For this reason, an additional 10% of the patients are expected to be prematurely withdrawn. This leads to a total attrition of approximately 43% ($= 1 - (1-0.255) \times (1-0.15) \times (1-0.10)$) over 3 years.

Expected Attrition in patients with left ventricular leads
Withdrawals due to deaths

In the RHYTHM ICD/QuickSite 1056K left heart lead study, the annual mortality was 12.8%, providing an estimated mortality rate of 33.7 % $[1 - (1-0.128)^3]$ at 3 years.

Withdrawals for reasons other than death

In the ongoing St. Jude Medical post-approval study, the attrition rate due to reasons other than death at 22 months of follow-up is 9%. Thus, it is anticipated that the attrition rate at 3 years for reasons other than death will be 15%.

Assuming that deaths and withdrawals are independent events, the total attrition is expected to be approximately 43.6% ($= 1-(1-0.337) \times (1-0.15)$) over 3 years.

Table 2: Enrollment in Lead Subgroups

Lead Group	Age of Lead at Enrollment (Years)	Min Enrollment	Expected Attrition at 3 years*	Target Enrollment
Riata Silicone	≥ 7	100	47%	195
	≥ 6 and < 7	100	45%	185
	< 6	100	43%	180
Riata ST	≥ 5.5	100	45%	185
	< 5.5	100	43%	180
QuickSite 1056T/1058 and QuickFlex 1156T/1158T	≥ 6	115	46%	225
	≥ 5 and < 6	115	46%	225
	< 5	170	44%	300
Durata	≥ 5	167	37%	275
	≥ 4 and < 5	167	37%	275
	< 4	167	37%	275

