- It is recommended that the Stored EGM Configuration be programmed to the following in patients with

Current/Promote or newer devices ICDs and CRT-Ds:

- RV Bipolar
- RV Unipolar Tip
- Custom: RV Coil to Can (optional)

*** Note:** If patient is pacer dependent or R-wave is not available then RV signal amplitude is not required.

Upon completion of the enrollment visit, complete the enrollment case report form (CRF) using the EDC system and submit the supportive data listed below to St. Jude Medical. Contact and address information are available on the last page of the CRF worksheet.

Enrollment CRF

Electronic device session records

Cinefluoroscopy (AP, LAO 45° or best possible LAO view, RAO 45° or best possible RAO view)

Earliest Chest X-ray or imaging study with evidence of externalized conductors or other visual lead anomalies, if available

Latest Chest X-ray or imaging study with no evidence of externalized conductors or other visual lead anomalies, if available

All eligible patients will be required to undergo the protocol specified follow-up visits. Patient participation in the study will be terminated once the 36 month visit is completed or after all leads being followed by the study are extracted and/or abandoned and the patient is monitored for 30 days.

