3.4.3 System Revision

All pulse generator and lead related system revisions should be reported. If a patient's existing Riata, Riata ST, QuickSite (1056T/1058T), QuickFlex (1156T/1158T), or Durata lead is extracted or capped, and no other of the above mentioned leads are still implanted then the patient will be followed for 30 days and withdrawn from the study. It is recommended to provide fluoroscopy data, RV (if applicable) and LV (if applicable) capture threshold, pacing impedance and signal amplitude measurements, and session records at system revision.

Upon completion of system revision, complete the following case report forms using the EDC system and submit the supportive data listed below:

- System Revision
- Product Out of service (if applicable)
- Device session records
- Fluoroscopy/ CXR images (if applicable)
- Adverse Event CRF
- Withdrawal CRF (if applicable)
- Supporting documentation of adverse events, deviation(s) from the protocol, and/or death

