11.3 Electrical Data Adjudication Committee

Electrical Data Adjudication Committee (EDAC) will be comprised of at least three Electrophysiologists or Cardiologists experienced in analyzing and interpreting device data. The role of the EDAC is to adjudicate the device session records to determine the presence of electrical dysfunction in the SJM Cardiac Lead Assessment study patient population. Committee members will be reviewing device session records for all leads taken out of service during the course of the study. Data will be sent either electronically or in a paper binder to the committee members. Once the adjudication is complete, an electrical data adjudication form will be collected per patient.

Only the adjudicated cases of electrical dysfunction will be included in the post market surveillance reports. Percentage of leads with electrical dysfunction (based on the definition in section 2.0) will be part of the reports.

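### Section 3.2.2.10, endpoints 1-2: the chi-square comparison ignores that leads counted as dysfunctional leave service and so have fewer scheduled cines

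*Combined protocol and SAP*

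**What the plan says.** In section 3.2.2.10, endpoint 1 reads "Frequency of externalized conductors. This will be done using a" Pearson chi-square; endpoint 2 does the same for other visual anomalies. Neither gives a time window, a count of cines or an adjustment for follow-up. Endpoints 3-4 compare time to detection by Kaplan-Meier without a censoring rule of their own.

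Four other parts of the plan bear on this:

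- **Definition (2.0).** Dysfunction is an adjudicated failure after which the lead was "surgically capped/extracted or electrically abandoned". Section 11.3 matches: "Committee members will be reviewing device session records for all leads taken out of service during the course of the study".
- **End of follow-up.** Participation ends at 36 months or "after all leads being followed by the study are extracted and/or abandoned and the patient is monitored for 30 days" (3.4.1). If no other study lead remains implanted, "then the patient will be followed for 30 days and withdrawn from the study" (3.4.3).
- **Imaging.** Cines are scheduled at enrollment and at 12, 24 and 36 months, with month 48 for extended QuickSite/QuickFlex patients. After a significant electrical abnormality, "x-ray or cinefluoroscopy would be performed as per the site standard of care" (3.1). At revision, "It is recommended to provide fluoroscopy data" (3.4.3). Section 11.2 has extra cines adjudicated along with the scheduled ones.
- **Censoring (3.2.2.1-3.2.2.2).** Time to externalization, or to another anomaly, is censored 3 years after enrollment.

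**The concern.** The grouping variable cuts short the chance to observe the outcome. A lead that fails and is removed in month 10 has had one scheduled cine; a lead that works throughout has had four. Externalization that begins after enrollment is more likely to be seen in the second lead, whatever its relation to electrical failure. A chi-square on ever-detected frequency counts that difference as part of the association.

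Section 1.0 promises physicians information on whether externalization with normal function progresses to malfunction. The main analysis for that is 3.2.2.4, but it follows only leads that already have externalization. Endpoints 1-2 of 3.2.2.10 add the contrast with leads that do not. As planned, unequal imaging alone could make externalization look slightly protective when there is no link, or shrink a real link.

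**Working it through.** **1. Attrition (section 3.1).** 1 − (1 − 0.255)(1 − 0.15)(1 − 0.10) = 43.0% at 3 years for Riata/Riata ST, which matches the plan. As a constant hazard this is −ln(0.57)/3 = 0.187 per year.

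**2. Assumptions not in the plan.** Dysfunction 3% per year; one study lead per patient; constant hazards; new externalization at −ln(1 − p)/6 per year, where p is enrollment prevalence and 6 is assumed implant years. Section 1.0's reported range of 0.5% to 33.3% for p gives 0.08% to 6.8% per year.

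**3. Scheduled cines per lead.** Let L = 0.187 + 0.03 = 0.217 and S(t) = exp(−Lt), so S(1), S(2), S(3) = 0.805, 0.647, 0.521.

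- With dysfunction, the chance of still being followed at year t is [S(t) − S(3)]/[1 − S(3)], which is 0.592, 0.264 and 0. Expected cines: 1 + 0.592 + 0.264 = 1.86.
- The chance of observed dysfunction within 3 years is (0.03/L)(1 − 0.521) = 0.066.
- Without dysfunction, the chance is [S(t) − (0.03/L)(S(t) − S(3))]/(1 − 0.066), which is 0.820, 0.675 and 0.558. Expected cines: 1 + 0.820 + 0.675 + 0.558 = 3.05.

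**4. Odds ratio with no link, at p = 10%.** The externalization hazard is −ln(0.9)/6 = 0.0176 per year. Detected frequency is 1 − 0.9 × E[exp(−0.0176 × year of last cine)].

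- With dysfunction, the last cine falls at year 0, 1 or 2 with chance 0.408, 0.328, 0.264: frequency 11.3%.
- Without, at year 0, 1, 2 or 3 with chance 0.180, 0.145, 0.117, 0.558: frequency 13.2%.
- Odds ratio: (0.1133/0.8867)/(0.1317/0.8683) = 0.84.

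**5. Simulation over the prevalence range, with the ±60-day visit windows.**

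| Scenario | Odds ratio, no link | Odds ratio, true doubling |
|---|---|---|
| Base case | 0.82-0.87 | 1.63-1.77 |
| Image at every failure | 0.89-0.92 | 1.83-1.88 |
| 40% stay on schedule because of a second study lead (assumed) | 0.92-0.93 | 1.79-1.87 |
| Implant age 4-8 years, dysfunction 1-5%/yr, attrition 37-47% | 0.72-0.90 | 1.41-1.83 |
| p = 10%, new cases 5%/yr | 0.70 | 1.37 |

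The time-updated rate ratio in the base case is 1.00-1.02 with no link and 1.95-2.03 with a doubling. By enrollment-cine status it is 1.00-1.02 and 1.85-2.03.

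**6. Removal prompted by the image, no biological link.**

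- *Explant of a normally functioning lead.* Not dysfunction under section 2.0, so the lead joins the comparison group. At 25% prevalence, about 10% of leads explanted and 37% other attrition, the odds ratio is about 0.62; the rate ratio stays near 1.0.
- *Removal counted as dysfunction and made more likely by a known externalization.* At 1.2-fold the odds ratio is 0.99-1.01 and the rate ratio 1.19-1.21. At 1.5-fold they are 1.24-1.30 and 1.50-1.52.

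**7. Endpoint 3.** With no link, counting every failure-prompted image gives a hazard ratio of 1.53-1.55. Censoring at the calendar date of the last image gives 1.43-1.49, an artefact of the visit windows. Counting time in scheduled visits gives a detection ratio of 0.98-1.00, and 1.83-1.99 with a doubling.

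**8. Precision.** The Riata target is 195 + 185 + 180 = 560 leads. At 3% per year, 560 × 0.066 = 37 dysfunctions are expected; at 1% per year, about 13. With 10 of 37 in leads with detected externalization (25% prevalence), the 95% limits are a factor exp(1.96√(1/10 + 1/27)) = 2.1 either side. With about 1.4 of 13 (10% prevalence), exp(1.96√(1/1.4 + 1/11.6)) is about 5.7.

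**The case against.** The strongest objection is that this matters little. Section 3.2.2.10 carries no alpha, power or decision rule, and a shift from 1 to 0.82-0.87 is small beside limits of a factor 2.1-5.7. That stands, and it sets the weight of the point.

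A reader might infer that the chi-square is badly miscalibrated. Simulated false-positive rates at a nominal 5% reach 14-74%, but only with all 2,110 projected enrollments pooled, new externalization assumed at 3-10% per year and no image at failure. Section 3.1 treats lead groups separately; at 500 leads the range is 0.4-21%. The documents do not support the stronger reading.

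A reader might also infer a known direction. Section 3.1 says of Riata/Riata ST leads that "it is more likely that some physicians will explant them, even when electrical function is normal". Those leads fall in the comparison group, so if the image prompts the explant the odds ratio goes down; the sentence is no evidence for an upward shift. Removals that count as dysfunction could push it up. How often either occurs is not stated, so the net direction is unknown.

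Nor is the plan silent on fault-prompted cines or on censoring. Section 11.2 has extra cines adjudicated, and 3.2.2.1-3.2.2.2 give a 3-year rule for the same variables. What is missing is how 3.2.2.10 uses the extra images. Applied literally, the 3-year rule would keep a removed lead at risk after imaging has stopped.

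Finally, a rate ratio is not a purely biological estimate. In the 1.2-fold scenario it lies further from 1 than the odds ratio. It also needs lead age: if both hazards rise with age over 3-9 years (assumed), a ratio not stratified by age is 1.14-1.16 with no link.

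**Conclusion.** The point holds as a modest analysis defect in a descriptive secondary outcome. Following the plan as written gives an association biased by unequal imaging: about 1.9 against 3.05 scheduled cines, an odds ratio of 0.82-0.87 with no link, and 1.63-1.77 for a true doubling. Images at failure and second study leads reduce this but do not remove it. If frequency were meant as enrollment-cine status only, the unequal number of cines would not arise, but the text does not say so.

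The sizes rest on the assumed 3% dysfunction per year, constant hazards, and new externalization matched to prevalence over six implant years. The attrition, target size and prevalence range are the plan's. The existence of the imaging deficit rests only on the plan's own definition, withdrawal rule and cine schedule.

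**What to change.** - **Endpoints 1-2.** Replace the chi-square with dysfunction rates per lead-year by time-updated externalization (or anomaly) status from scheduled adjudicated cines, within lead group. Give one rate ratio stratified by lead group and adjusted for lead age at enrollment, using the Table 2 categories, coarsened if events are few.
- **Check.** Report the same rate comparison by enrollment-cine status, where every lead has had one cine, and show the number of cines per group.
- **Caveat beside the result.** State that the rate ratio removes the unequal-imaging bias but not the effect of image-prompted removal that is counted as dysfunction.
- **Endpoints 3-4.** Do not carry over the 3-year censoring rule to leads that left service. End each lead's time at risk at its last adjudicated scheduled cine, count time in scheduled visits, and report fault-prompted images separately. Section 3.2.3 already collects the type of event leading to detection.

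The cost is a wording change in the next protocol revision, plus programming. No new data are needed. The downside is few events and wide intervals, as step 8 of the working shows.
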